4.2.4 Replacements

Participants who withdraw or are withdrawn from the study within 4 weeks of randomization may be replaced in order to have approximately 225 participants provide at least 4 weeks of postbaseline data.

Replacement participants will be randomly assigned treatment in the respective cohorts of the participants they replace.

5 Study Treatments

5.1 Method of Assigning Participants to Treatment Groups

Participants will be randomly assigned at the baseline visit (Visit 2) to 1 of 3 cohorts (in a 1:1:1 allocation ratio) that are distinguishable to participants and study staff by the number of capsules administered per once-daily dose. Within the cohort, participants will be randomly assigned in a 2:1 allocation ratio to receive either EDP1815 or matching placebo treatment (Section 3.1). Interactive response technology will be used to administer the randomization schedule.

5.2 Treatments Administered

Participants in each cohort (described in Section 3.1) will self-administer study drug doses orally in the morning with water, refraining from consuming acidic drinks 1 hour either side of dosing and from eating 2 hours before dosing and 1 hour after dosing (Table 6-1). The composition of capsules is described in Section 5.3. Strategy to improve compliance is presented in Section 5.7.

5.3 Identity of Study Drug

The EDP1815 drug product is available as enteric-coated HPMC hard capsules in Swedish-Orange color. The EDP1815 PIC consists of freeze-dried powder of *P histicola*, mannitol, magnesium stearate, and colloidal silicon dioxide. Each EDP1815 PIC contains 8.0×10^{10} cells of *P histicola*.

The matching placebo is identical in appearance but do not contain *P histicola* or any other bacteria. The placebo excipients include microcrystalline cellulose and magnesium stearate.

5.4 Management of Clinical Supplies

5.4.1 Study Drug Packaging and Storage

EDP1815 PICs and matching placebo will be prepared in blister wallets of 10 capsules. Blister wallets will be packaged in packs that contain approximately 1 week's supply of study drug for 1 randomized participant, identified by a numeric code. When appropriate for the interval between study visits, multiple packs will be assigned and dispensed for each participant throughout the treatment period.

Study drug (EDP1815 and placebo) must be stored in a secure area (eg, a locked refrigerator) and kept at a controlled temperature of 2°C to 8°C. The investigator or designee must confirm appropriate temperature conditions have been maintained during transit and during storage at each site for all study drug received and any discrepancies are reported and resolved before use of the study drug.

██████████ will supply study drug to each site in non-study descript shipping containers that will maintain temperature during transit within 2°C to 8°C. Temperature monitoring devices will be used to confirm adequate transit temperature. Site procedure for receipt of study drug will be provided in the IMP handling manual.

5.4.2 Study Drug Accountability

The investigator will maintain accurate records of receipt of all study drug, including dates of receipt. In addition, accurate records will be kept regarding when and how much test article is dispensed and used by each participant in the study. Study drug will be assigned using an IRT system. Only participants enrolled in the study may receive the study drug and only authorized site personnel may supply the study drug. Reasons for departure from the expected dispensing regimen must also be recorded. At the completion of the study, to satisfy regulatory requirements regarding drug accountability, all study drug will be reconciled and retained or destroyed according to applicable regulations. Further guidance and information for the final disposition of unused study drug are provided in the IMP handling manual. Accountability, reconciliation, and then shipment for destruction or for destruction on site will be documented through the IRT.

5.4.3 Other Supplies

Evelo will supply Bristol stool diaries (Section 6.2.2) and paper dosing diaries to all participants (Section 5.7.1). Electronic devices for administering questionnaires will be provided to all study sites.

5.5 Overdose Management

An overdose is any dose of study treatment given to a participant or taken by a participant that exceeds the maximum dose described in the protocol (10 capsules per day).

Participants will be instructed to contact the investigator or study coordinator immediately in the event of a suspected overdose. In the event of overdose, the appropriate supportive clinical care must be provided as dictated by the participant's clinical status.

Any overdose must be promptly reported to [REDACTED]. Overdose itself is not to be reported as an AE. However, any AEs or SAEs associated with the overdose are to be reported on relevant AE/SAE sections in the eCRF and on the Paper SAE Form provided to [REDACTED] (Section 6.2.1).

In the event of a symptomatic overdose, the investigator should:

1. Contact the medical monitor immediately.
2. Document the quantity of the excess dose in the eCRF.
3. Document the overdose symptoms and their duration in the eCRF.

Decisions regarding dose interruptions or modifications will be made by the investigator in consultation with the medical monitor based on the clinical evaluation of the participant.

5.6 Blinding

Study drug will be double-blinded. All study drug (EDP1815 and placebo) will be supplied in identical packaging, color, smell, and appearance to enable double-blinded conditions that ensure all investigators, study site staff, participants, and clinical monitors will remain blinded throughout the study. The IRT system will assign study drug to participants at the time of randomization. Only personnel supporting the IRT system, the independent randomization team, and clinical supplies will be unblinded and will have access to treatment assignments; all other parties involved in the study will be fully blinded.

For the interim analysis, unblinded aggregate results will be produced by an unblinded team within [REDACTED] and reviewed by Evelo personnel for strategic planning use. These will not be shared with any study site staff, participants, or clinical monitors who will be involved in the collection and review of individual study data.

The data will be unblinded and the primary analysis will be performed once all participants have completed 4 weeks of post-treatment follow-up at Visit 11 (Week 20; at the end of

Part A). Study site staff, participants, and clinical monitors who will be involved in the collection and review of individual study data will remain blinded until Part B is completed.

5.6.1 Breaking the Blind

A participant's treatment assignment will not be unblinded for the investigator or study site staff until EOS unless medical treatment of the participant depends on knowing the study treatment the participant received. In the rare event that unblinding is needed because of a medical emergency, the investigator may unblind an individual participant's treatment allocation through the IRT. In case of an emergency, the investigator has the sole responsibility for determining if unblinding of a participant's study treatment assignment is warranted. Participant safety must always be the first consideration in making such a determination. If the investigator decides that unblinding is warranted, the investigator should make every effort to contact the sponsor prior to unblinding a participant's study treatment assignment unless this could delay emergency treatment of the participant. If a participant's study treatment assignment is unblinded, the sponsor must be notified within 24 hours after breaking the blind. Reasons for treatment unblinding must be clearly explained and justified in the eCRF. The date on which the code was broken together with the identity of the person responsible must also be documented.

Participants who are unblinded will be allowed to continue their participation in the study; however, any data collected after the unblinding occurred will be excluded from per-protocol analyses.

The Clinical Safety team at [REDACTED] will be unblinded to study treatment to facilitate appropriate identification and reporting of SUSARs to Competent Authorities and the relevant IECs/IRBs.

5.7 Compliance With Study Treatment

Participant compliance will be determined from capsule counts of unused capsules according to the SoA (Table 6-1).

At each visit during the treatment period (Visit 2 through Visit 9), study site staff will remind the participant of the need to self-administer the capsules as directed and store the study drug according to label instructions.

Before each visit (Visit 3 through Visit 10), study site staff will call participants to remind them to bring all study drug in the original containers to the study site for their visit, and to remind them to also bring their dosing diaries (Section 5.7.1).

Compliance will be assessed by counting returned capsules during the site visits indicated in the SoA (Table 6-1), and the counts will be documented in the source documents and eCRF. Deviation from the prescribed dosage regimen should be recorded in the eCRF.

A record of the number of study drug capsules dispensed to and taken by each participant must be maintained and reconciled with the study drug and compliance records. Study treatment start and stop dates, including dates for study treatment delays and/or dose reductions, will also be recorded in the eCRF.

5.7.1 Dosing Diaries

The primary purpose of the diary is to enhance participant compliance with the protocol. Participants will be asked to capture the following information in the diaries:

- Dates of dosing with study drug
- Times of dosing with study drug
- Numbers of capsules in dose
- Changes in concomitant medications
- Changes in symptoms
- Other comments

Diaries will be dispensed and collected as detailed in the SoA (Table 6-1). Study staff will review the diaries with participants at each visit when diaries are collected. Diaries will be reviewed for completeness and accuracy, and participants will be coached as needed on compliance with the protocol.

5.8 Prior, Concomitant, and Rescue Medications

Use of all concomitant medications will be recorded in the participant's eCRF. The minimum requirement is that drug tradename, total daily dose, and the dates of administration are to be recorded. In addition, it is expected that the reason for use and dosage information (including dose and frequency) will also be recorded. This will include all prescription drugs, herbal products, vitamins, minerals, and OTC medications. Any changes in concomitant medications also will be recorded in the participant's eCRF. The participant's dosing diary may contain information relevant to the documentation of changes in concomitant medication.

Any concomitant medication or therapy deemed necessary for the welfare of the participant during the study may be given at the discretion of the investigator. However, it is the responsibility of the investigator to ensure that details regarding the medication are recorded in full in the eCRF.

5.8.1 Prior Therapy

Prior therapies restricted for participants eligible for this study are detailed in the exclusion criteria (Section 4.1.2).

5.8.2 Concomitant Therapy

Anti-histamines and acetaminophen/paracetamol following labeled dosing instructions are permitted for use at any time during the study. Topical unmedicated emollients and low-potency topical steroids are also permitted if participants were already using them as part of their care prior to study entry (exclusion criterion #10, Section 4.1.2). Participants will be advised to continue to use these therapies as they were prior to study entry.

Non-live and non-replicating vaccines are permitted in this study.

Other concomitant medication may be considered on a case-by-case basis by the investigator in consultation with the medical monitor if required.

5.8.2.1 Prohibited Concomitant Therapy

Prior therapies restricted for participants eligible for this study as detailed in the exclusion criteria (Section 4.1.2) are prohibited concomitant therapy during the study.

Live or live-attenuated replicating vaccines are contra-indicated in this study.

5.8.3 Rescue Medicine

Although *P. histicola* is a natural human commensal in the human GI tract, if a rare overgrowth condition is suspected the following rescue antibiotics may be used (supplied by the study site) if the clinical situation warrants such use:

1. Penicillin V
2. Amoxicillin

Or, if allergic to the above antibiotics:

3. Macrolides (eg, clarithromycin or erythromycin)
4. Tetracyclines (eg, doxycycline)

The date and time of rescue medication administration as well as the name and dosage regimen of the rescue medication must be recorded in the eCRF.

5.9 Dose Modification

Dose adjustments, including dose interruptions, and/or decreasing the dose frequency may be allowed for safety or tolerability (including capsule load) after consultation with the sponsor medical monitor.

6 Study Assessments and Procedures

Before performing any study procedures, all potential participants will sign an ICF.

Additional procedural details related to the ICF are provided in Section 9.3.

The SoA is presented in Table 6-1. Detailed instructions for study site activities will be provided in the appropriate specific user manual, where applicable. High level descriptions of the study assessments are presented in the subsections of Section 6. In exceptional circumstances, study assessments may be conducted remotely (ie, at a participant's home), except for screening, baseline, Visit 9, and Visit 10. Remote visits can only occur if operationally possible.

Table 6-1 Schedule of Assessments – Part A

Procedure	Screening	Baseline	Treatment Period								Follow-up ^{a, b}
Day	-28 to -7	1	8	15	22	29	43	57	85	113	141
Week	-4	0	1	2	3	4	6	8	12	16	20
Visit number	1	2	3	4	5	6	7	8	9	10	11
Visit window (days)	--	--	5-11	12-18	19-25	26-32	40-46	54-60	82-88	110-116	141-148
Informed consent	X										
Inclusion and exclusion criteria	X	X ^c									
Demography	X										
HbsAg, HCV and HIV screening	X										
HLA sample ^d		X									
Medical history and current medical conditions (including duration of psoriasis)	X	X									
Full physical examination (height only at screening) ^e	X	X	X			X			X	X	X
Pregnancy test ^f	X	X								X	X
Laboratory assessments (hematology, serum biochemistry and CRP, and urinalysis)	X	X				X		X	X	X	X
Fasting ^g blood sampling		X						X		X	
12-lead ECG ^h	X	X				X				X	X
Vital signs ⁱ	X	X	X	X	X	X	X	X	X	X	X
Randomization		X									
Dosing ^j		X	X	X	X	X	X	X	X		
Dispense study drug		X	X	X	X	X	X	X	X		
Collect/count unused study drug			X	X	X	X	X	X	X	X	
Skin plaque biopsies ^k		X								X	

Procedure	Screening	Baseline	Treatment Period								Follow-up ^{a, b}
Day	-28 to -7	1	8	15	22	29	43	57	85	113	141
Week	-4	0	1	2	3	4	6	8	12	16	20
Visit number	1	2	3	4	5	6	7	8	9	10	11
Visit window (days)	--	--	5-11	12-18	19-25	26-32	40-46	54-60	82-88	110-116	141-148
Digital photography of lesion sites ¹		X				X		X		X	X
Stool samples for microbiome investigation ^m		X								X	X
Dispense stool diary	X										
Collect/record stool diary		X									
Blood sample for detection of systemic EDP1815		X								X	
Samples for blood biomarkers		X								X	
BSA involvement (%), PGA, PASI ^{n, o}	X	X	X	X		X		X	X	X	X
LSS, mNAPSI ⁿ		X	X	X		X		X	X	X	X
PSI, DLQI, PA-VAS, SF-36 (vitality and pain), Fatigue ^p		X	X	X		X		X	X	X	X
AE/SAE review	X	X	X	X	X	X	X	X	X	X	X
Concomitant medication review	X	X	X	X	X	X	X	X	X	X	X
Dispense dosing diary		X	X	X	X	X	X	X	X		
Collect/review dosing diary ^q			X	X	X	X	X	X	X	X	

^a Participants who withdraw from the study during Part A should complete the final assessments listed under the Follow-up Visit (Week 20), at an unscheduled follow-up visit. Where relevant and when possible, this should be arranged within 72 hours of the start of a new psoriasis treatment. In the event of early withdrawal from the study, unused study drug is to be collected/collected at this visit.

^b All participants will attend additional follow-up Visits 12 and 13 (see Table 6-2), unless they are considered a 'treatment failure' or meet the criteria for rebound.

^c Recheck inclusion/exclusion criteria at Baseline, before first dose of study drug. Screening laboratory results will be used to confirm eligibility at Baseline/Visit 2 (ie, Day 1).

^d Predose optional genetic samples.

- e BMI will be calculated from the height and weight.
- f Women of child-bearing potential only. Serum HCG at screening, urine thereafter. Pregnancy testing will be performed at the visits indicated or if a menstrual cycle is missed or if pregnancy is otherwise suspected.
- g Participants will fast for at least 8 hours before glucose and lipid blood sampling
- h A single ECG tracing is to be obtained on the day of the visit. If, in the opinion of the investigator, there appear to be clinically significant findings, a second tracing should be obtained during the visit.
- i Blood pressure, pulse, respiratory rate, and temperature are to be checked on the day of the visit.
- j The first dose will be given at the baseline visit, following random assignment to treatment. Subsequent doses are to be taken (away from the study site) once daily in the morning at approximately the same time ± 2 hours. Participants should refrain from consuming acidic drinks 1 hour either side of dosing and from eating 2 hours before dosing and 1 hour after dosing. On days of study site visits during the treatment period (Visit 3 through Visit 10, inclusive), participants may dose at home.
- k Skin plaque biopsies (ie, a 4 mm punch biopsy, performed pre-dose by suitably trained study personnel and processed as per laboratory manual) are to be performed after all other assessments have been completed at the end of Visits 2 and 10.
- l Digital photographs should be taken of up to 6 lesion sites that have a lesion area ideally greater than 2 cm by 2 cm at baseline. The same locations photographed at baseline should be followed throughout the study for each participant.
- m Stool samples are to be collected within the 48 hours preceding each visit of stool sample collection.
- n Investigator rating scales. Participants will be asked to withhold all emollients or moisturizers on the day of these study visits until all study assessments are completed.
- o Inclusion criterion #4 (mild to moderate plaque psoriasis with plaque covering BSA of $\ge 3\%$ and $\le 10\%$, PASI score of ≥ 6 and ≤ 15 , and PGA score of 2 or 3) should be reconfirmed at the baseline visit prior to randomization.
- p Participant-reported assessments.
- q Study staff will review the dosing diaries with participants at each visit when diaries are collected. Diaries will be reviewed for completeness and accuracy, and participants will be coached as needed on compliance with the protocol.

Table 6-2 Schedule of Post-Treatment Follow-Up Assessments – Part B

Procedure	Post-Treatment Follow-Up – Part B ^a			Early Withdrawal Visit ^a
Visit number	12^b	13^b	14^c	
Months (after the End of Treatment)	2	3	6	
Weeks	24	28	40	
Day	169	197	218	–
Visit window (days)	162-176	190-204	204-232	–
BSA involvement (%), PGA, PASI ^d	X	X	X	X
LSS, mNAPSI ^d	X	X	X	X
PSI, DLQI ^e	X	X	X	X
Concomitant medication review	X	X	X	X

^a Participants who withdraw from the study during Part B should complete the final assessments at the Early Withdrawal Visit (where relevant and when possible, this should be arranged within 72 hours of the start of a new psoriasis treatment).

^b All participants will attend Visits 12 and 13, unless they are considered a ‘treatment failure’ or meet the criteria for rebound.

^c Only participants who are classified as responders at Week 16 (Visit 10) and have not relapsed at Week 28 (Visit 13) will be eligible for Visit 14 (Week 40).

^d Investigator rating scales. Participants will be asked to withhold all emollients or moisturizers on the day of these study visits until all study assessments are completed.

^e Participant-reported assessments.

During the screening period, participants will be advised to monitor their psoriasis symptoms and remain on a stable regimen of topical emollients and low-dose topical corticosteroid medications (if they are already taking any). Participants will be asked to withhold the application of any emollients or moisturizers on the day of any site visit until after all study assessments have been performed. As part of the screening, PASI, BSA involvement, and PGA scores will be measured (inclusion criterion #4, Section 4.1.1).

Participants meeting eligibility criteria at screening will return to the study site on Day 1. The PASI, BSA involvement, and PGA scores must be available to reconfirm eligibility prior to randomization and administration of the first dose of study drug on Day 1 (Visit 2).

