3.1 Study Design

This is a multicenter, randomized, double-blind, placebo-controlled, parallel-cohort, dose-ranging study of participants with mild to moderate plaque psoriasis (Section 4.1).

Part A of the study comprises a screening period of up to 4 weeks, a baseline visit, a treatment period of 16 weeks (8 planned study site visits), and a follow-up visit at Week 20 (4 weeks after cessation of dosing). Part A of the study therefore comprises a total of 11 scheduled study visits, and on completion of Part A, the primary analysis will be performed.

Part B of the study is designed to assess the durability of treatment response and incidence of rebound of psoriasis following cessation of dosing. All participants will attend for skin assessments at Weeks 24 and 28, unless they have previously experienced treatment failure and/or had rebound of disease. A final visit at Week 40 will also be performed for those participants who experienced treatment response at Week 16 of treatment, but have not yet met the definition of disease relapse. Part B of the study therefore comprises a maximum of 3 additional scheduled study visits with a follow-up of up to 40 weeks (24 weeks after cessation of dosing), and on completion of Part B, the final analysis will be performed.

The study design is presented in Figure 3-1, and the SoA is presented in Table 6-1 for Part A, and in Table 6-2 for Part B.

After eligibility is confirmed during the screening period (Section 4.1), participants will be randomly assigned in a 1:1:1 ratio to 1 of the following 3 parallel cohorts:

- Cohort 1: 0.8×10^{11} cells of EDP1815 or matching placebo administered as 1 PIC, once daily (Section 5.2).
- Cohort 2: 3.2×10^{11} cells of EDP1815 or matching placebo administered as 4 PICs, once daily (Section 5.2).
- Cohort 3: 8.0×10^{11} cells of EDP1815 or matching placebo administered as 10 PICs, once daily (Section 5.2).

In each cohort, approximately 75 participants will be randomly assigned in a 2:1 ratio to receive either EDP1815 or matching placebo once daily for 16 weeks.

[figure not shown]
An interim analysis may be performed after at least 50% of participants have completed at least 12 weeks of treatment (Section 7.6.7).

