9.5.6 Partial Relapse, Relapse and Rebound

The following endpoints will be summarised by treatment group and visit in the

- Week 16 responders population:
 - Cumulative incidence of partial relapse at Weeks 20, 24, 28, and 40
 - Cumulative incidence of complete relapse at Weeks 20, 24, 28, and 40
- mITT population:
 - Cumulative incidence of rebound at Weeks 20, 24, 28, and 40

These summary tables will include the number of participants meeting the criteria for the endpoint, and the number of participants 'at risk' of meeting the criteria (the denominator for the cumulative incidence i.e. excluding any participants with a missing status for that endpoint).

For each endpoint, the cumulative incidences for each treatment group will be plotted against time (Week 20 to Week 40) as bars (with an 'error bar' for the corresponding 95% CI).

No inferential analysis of relapse or rebound will be carried out.

Table 6 Intercurrent Event Strategies for Partial Relapse, Relapse and Rebound Endpoints

Endpoint	Intercurrent event	Strategy to account for intercurrent event
Partial Relapse and (Complete) Relapse	Starting a new psoriasis treatment	Composite Starting a new psoriasis treatment is part of the endpoint definition

Endpoint	Intercurrent event	Strategy to account for intercurrent event
Rebound	Starting a new psoriasis treatment	
While in the period following cessation of study treatment, without taking a new psoriasis treatment (analogous to While on treatment)
 
Rebound status will be considered missing from 4 days after the day a new psoriasis treatment is started, onwards, and will not be counted in the denominator during calculation of cumulative incidences

Note that, according to the study design, starting a new psoriasis treatment (synonymous with study treatment failure) should result in a subject completing a PASI questionnaire at an unscheduled Follow-up (Part A)/Early Withdrawal (Part B) visit within 72 hours and then being withdrawn from the study. The above strategies for dealing with the intercurrent event of starting a new psoriasis treatment are included to cover the possibility of a protocol deviation occurring whereby a participant is not withdrawn from the study within 72 hours following the start of a new psoriasis treatment, and to clarify the estimand for rebound.

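### Protocol Table 6-2 schedules the Week 40 visit on Day 218 (window 204-232), which is Week 31; on the table's own rule Week 40 is Day 281

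*Protocol*

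**What the plan says.** Protocol Table 6-2 (Part B schedule) gives Visits 12, 13 and 14 as Weeks 24, 28 and 40. Its other rows for the same three visits are:

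- Months: "Months (after the End of Treatment) 2 3 6"
- Days: "Day 169 197 218"
- Windows: "162-176 190-204 204-232"

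Footnote c of the table also calls Visit 14 the Week 40 visit, and limits it to Week 16 responders who have not relapsed at Week 28.

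Protocol 3.1 describes Part B as "follow-up of up to 40 weeks (24 weeks after cessation of dosing") and gives a maximum participation of 44 weeks, which is 4 weeks of screening plus 40. Protocol 3.1.1 and SAP 5.1 also place the last visit at Week 40.

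SAP 9.5.6 lists "Cumulative incidence of complete relapse at Weeks 20, 24, 28, and 40" among the Part B summaries, with partial relapse and rebound at the same weeks. SAP 7.7 assigns data to nominal visits. It records an out-of-window visit as a protocol deviation but keeps its data in the tables.

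**The concern.** The week and month rows of Table 6-2 put Visit 14 at one date, and the day and window rows put it at another about two months earlier. A site needs a date to book the visit, and the window row determines whether the visit counts as on schedule.

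Part B exists to measure durability after dosing stops, and Visit 14 is its last visit. Protocol 3.1 treats a participant as having completed the study once all required visits are done. If Visit 14 is held around Day 218, any relapse between then and Week 40 goes unobserved and would be hard to recover. If some sites follow the day and others the week, the Week 40 column mixes follow-up times about 9 weeks apart.

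**Working it through.** **1. The day rule.** The inputs are the Table 6-1 rows "Day -28 to -7 1 8 15 22 29 43 57 85 113 141" and "Week -4 0 1 2 3 4 6 8 12 16 20", and the Table 6-2 rows above. From baseline onward the rule is Day = 7 x Week + 1:

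| Week | 7 x Week + 1 | Printed day |
|---|---|---|
| 0 | 1 | 1 |
| 1 | 8 | 8 |
| 2 | 15 | 15 |
| 3 | 22 | 22 |
| 4 | 29 | 29 |
| 6 | 43 | 43 |
| 8 | 57 | 57 |
| 12 | 85 | 85 |
| 16 | 113 | 113 |
| 20 | 141 | 141 |
| 24 | 169 | 169 |
| 28 | 197 | 197 |
| **40** | **281** | **218** |

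The rule reproduces twelve of the thirteen printed days and fails only at Visit 14.

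**2. What the printed figures mean in weeks.**
- Day 218: (218 - 1)/7 = Week 31.0
- Window: (204 - 1)/7 = Week 29.0 to (232 - 1)/7 = Week 33.0

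**3. Size of the discrepancy.**
- Nominal day: 281 - 218 = 63 days, or 9 weeks early
- Across the window: 281 - 232 = 49 days to 281 - 204 = 77 days, or 7 to 11 weeks early
- Time after Week 16: (218 - 113)/7 = 15 weeks printed, against (281 - 113)/7 = 24 weeks intended
- Shortfall: 9/24 = 37.5%

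**4. Cross-checks within the protocol.**
- The month row counts 4-week months after Week 16: (24 - 16)/4 = 2, (28 - 16)/4 = 3, (40 - 16)/4 = 6. Week 31 would give 15/4 = 3.75, not 6.
- Visit 13 to Visit 14 is 218 - 197 = 21 days as printed. Week 28 to Week 40 is 12 x 7 = 84 days.
- The Visit 14 window opens on Day 204, the day the Visit 13 window closes ("190-204 204-232"), so one date satisfies both visits.
- Screening of 4 weeks plus 31 gives 35 weeks of participation, not 44.

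No alternative counting gives 218: 7 x 40 without the added day is 280, and six calendar months counted from Day 113 is about Day 296. The figure looks like 281 with its last two digits exchanged. The window is 218 plus or minus 14, so the slip carried into it.

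**5. Illustration of the effect on relapse.** The documents give no relapse rate. Assume a constant hazard after dosing stops and every Visit 14 held on Day 218. Observed incidence is then 1 - (1 - p)^(15/24), where p is the true 24-week incidence:

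| True at 24 weeks | Seen at 15 weeks, labelled Week 40 |
|---|---|
| 20% | 13% |
| 40% | 27% |
| 60% | 44% |

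**The case against.** The intended timing is stated many times over: the week row, the month row and footnote c of the same table, the study design text, and the SAP all say Week 40. Harm requires a site to follow the day or window row over all of these. The protocol leaves detailed site instructions to manuals that are not available here, so how sites actually scheduled is unknown. That stands, and the consequence is conditional on it.

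A correctly timed visit loses no data, because SAP 7.7 keeps out-of-window data. That also stands, but the same section means the erroneous visit is in window and labelled Week 40 while the correct one is logged as a deviation.

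The duration endpoints in SAP 5.3.3.4 use actual study day, so the mislabelling does not reach them. What remains is truncation: a participant whose effect has not ended is given the last PASI assessment as the end day, and that would fall 63 days sooner.

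The scope is narrow. Only Week 16 responders not relapsed at Week 28 attend, SAP 9.5.6 plans no inference on relapse or rebound, and the schedule is common to all arms. Rebound is defined within three months of stopping, so its Week 40 figure is little affected. The screening column does not fit the day rule, and the overlap at Day 204 is a by-product of the same error. These points limit the consequence. None of them supports Day 218.

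**Conclusion.** The Day and window entries for Visit 14 are wrong as printed. Week 40 is Day 281; the printed day is Week 31, which is 63 days early and leaves 15 of the 24 planned weeks off treatment. That arithmetic rests only on the protocol's own tables.

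The effect on results depends on how many sites used the printed day. Where they did, the Week 40 partial and complete relapse summaries would be understated, and unfinished durations cut by about nine weeks. The percentages in the illustration depend on the assumed relapse rates and constant hazard. The primary endpoint and the Part A analyses do not depend on this visit. The SAP does not repair the error, and its list of changes from the protocol (Table 8) does not mention it.

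**What to change.** - In Protocol Table 6-2, change the Visit 14 day to 281. If 14 days either side is kept, the window becomes 281 - 14 = 267 to 281 + 14 = 295, which also ends the overlap with Visit 13.
- Send sites a note with the corrected day and window.
- Add one line to SAP 7.7: any Visit 14 held on the basis of the printed window is analysed by its actual study day and not counted as a Week 40 assessment, and a visit at the true Week 40 is not treated as a deviation.

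The cost is one table correction, one site communication and one SAP sentence.
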